Appendix 6. Peripheral Blood Collection, Processing, and Shipping Instructions

Peripheral blood for measurement of serum testosterone, dihydrotestosterone, estradiol, and fasting insulin levels will be collected at each site according to the instructions outlined below, and shipped to a central laboratory for analysis. Specimens should be shipped within 1 month of date of collection.

Peripheral blood and urine collection for banking of peripheral blood mononuclear cells (PBMC), plasma, serum, and urine is optional. Specimens will be banked at a central laboratory.

I. Subject Confidentiality

Prior to the date of collection of each sample to be shipped to a central laboratory, the local CRC should notify the lead center CRC that specimen is to be collected at the subject's next visit. The lead center CRC will then assign unique specimen log numbers to be written on the specimen vials; this will ensure subject confidentiality.

A central laboratory will serve as a repository for banking human samples. The samples will receive a subject-insensitive identifier and the link to subject identity will be kept in a locked file with access only by the director of the Tissue Bank. Other investigators will have access to the samples only through established Tissue Core procedures. That is, investigators must submit a written request to use the stored samples as part of a CHR-approved protocol that is reviewed by the Tissue Core committee. This review limits the testing that can be done on these samples. Subjects have the right at any time to request that all remaining samples be destroyed. The subject or relatives may be contacted about future, additional research on stored samples, if necessary. Additional written consent will be required if additional samples are to be taken.

II. Serum Hormone Measurements

At baseline, after month 3, 6, 9, and 12, **fifteen** mL of whole blood will be collected in two red top tubes (no gel) and centrifuged at 3000 rpm for 10 minutes. The serum will be decanted into three 2mL polypropylene screw cap (leak-proof) vials that have been properly labeled with the unique specimen log numbers provided and stored at -80°C until shipment to a central laboratory.

After month 14, 16, 18, 20, 22, and 24, **five** mL of whole blood will be collected in one red top tube (no gel) and centrifuged at 3000 rpm for 10 minutes. The serum will be decanted into one 2 mL polypropylene screw cap (leak-proof) vial with the proper label and stored at -80°C until shipment to a central laboratory.

Serum testosterone, estradiol, and dihydrotestosterone levels will be measured in batched samples using liquid chromatography/tandem mass spectrometry (LC/MS/MS).

III. Fasting Plasma Insulin Measurement

At baseline, after month 3, 6, 9, 12, 18, and 24, **five** mL of whole blood will be collected in one red top tube (no gel) and centrifuged at 3000 rpm for 10 minutes. The serum will be decanted into one 2 mL polypropylene screw cap (leak-proof) vial that has been properly labeled with the unique specimen log numbers provided and stored at -80°C until shipment to a central laboratory.

IV. Banking of Peripheral Blood, Plasma, and Serum (Optional)

At baseline, after month 3, 6, 9, and 12, **twenty** mL of whole blood will be collected in one tigertop tube (serum) and one lavender top tube (plasma) and centrifuged at 3000 rpm for 10 minutes. The serum and plasma will be decanted into two 2mL polypropylene screw cap (leak-proof) vials (four total vials) that have been properly labeled with the unique specimen log numbers provided and stored at -80°C until shipment to a central laboratory.

At baseline, after month 3, 6, 9, and 12, urine should be collected and decanted into two 2mL polypropylene screw cap (leak-proof) vials labeled with the assigned specimen log numbers and stored in refrigerator until shipment to a central laboratory.

At baseline, **twelve** mL of whole blood in 2 plastic EDTA tubes will also be collected and freshly frozen at -80°C until shipment to a central laboratory.

V. Archival FFPE Blocks or Slides, Plasma and Whole Blood for Biomarker Testing (Optional)

Archival FFPE blocks or slides will be collected from consented subjects any time after enrolling into the study. Ship Archival FFPE blocks or slides ambient to a central laboratory. Whole blood samples will be collected at baseline end of treatment and progression. Blood (2.5ml) will be collected in PAXgene™ Blood RNA tube. PAXgene tube should be at room temperature ($18-25^{\circ}\text{C}$) prior to use. To prevent backflow, place donor's arm in a downward position. Hold tube in a vertical position, below the donor's arm during blood collection. Release tourniquet as soon as blood starts to flow into tube. Make sure tube additives do not touch stopper or end of the needle during venipuncture. Ensure that blood has stopped flowing into the PAXgene tube before removing the tube from the holder (at least 10 seconds). Gently invert the PAXgene tube 8-10 times. Always leave the PAXgene tube as the FINAL TUBE to draw. If the PAXgene tube is the only tube required, collect blood into a 2 mL discard tube prior to collecting the PAXgene tube. The discard tube must be filled with at least 2 mL of blood to flush the air from the tubing.

Be sure to follow complete PAXgene collection and sample handling instructions, which are provided with the tubes. Label tube with unique specimen identification numbers, which will be provided. Store samples at -80°C until shipped to a central laboratory.

Peripheral blood (10 ml) will be collected in K2EDTA tubes at end of treatment and progression. Centrifuge at room temperature for 10 minutes at 1600 (± 150) g. After centrifugation, transfer supernatant of the EDTA tube (using a disposable pipette) to one fresh 15 ml labeled centrifuge tube. Centrifuge the plasma in the 15 ml centrifuge tube at room temperature for 10 min at 3000 (± 150) g. After centrifugation, transfer supernatant to a fresh 15 ml centrifuge tube without disturbing the cellular layer using a disposable pipette. Be sure to pre-label this transfer tube. After transferring the plasma to a new 15 ml centrifuge tube as described, gently mix plasma.

Transfer 1ml plasma each into (2) 2ml labeled cryovials provided.

Place cryo tubes into a storage box and freeze upright. Store samples at -80°C until shipped to a central laboratory. Ship both aliquots (primary and back-up) together in your shipment.

VI. Shipping Instructions

Specimens may be batch-shipped on dry ice by overnight delivery Mondays-Thursdays. For specimens to be shipped to a central laboratory, the local coordinator should notify the lead center coordinator at the central laboratory prior to specimen shipment. As for the specimens to be shipped to a central laboratory (archival FFPE blocks or slides, plasma and whole blood for biomarker testing [optional samples]), please refer to the Central Laboratory Manual for the shipping instructions.

FACT-P	Functional Assessment of Cancer Therapy – Prostate
FDA	Food and Drug Administration
FFPE	formalin-fixed paraffin-embedded
HDL	high-density lipoprotein
HR	hazard ratio
IADT	intermittent androgen deprivation therapy
ITT	intent-to-treat
mITT	modified intent-to-treat
LDL	low-density lipoprotein
LHRH	luteinizing hormone-releasing hormone
LHRHa	LHRH agonist
MRI	magnetic resonance imaging
NCI	National Cancer Institute
NCIC	National Cancer Institute of Canada
OS	overall survival
PAB	peripheral androgen blockade
PBMC	peripheral blood mononuclear cells
PQC	product quality complaint
PSA	prostate-specific antigen

PSADT	PSA doubling time
QOL	quality of life
RT	radiation therapy
RTOG	Radiation Therapy Oncology Group
TSH	thyroid stimulating hormone
SHIM	Sexual Health Inventory for Men

1. INTRODUCTION

This document describes the planned statistical analyses for study protocol ARN-509-002 (The Role of Highly Selective Androgen Receptor (AR) Targeted Therapy in Men with Biochemically Relapsed (BCR) Hormone Sensitive Prostate Cancer). This statistical analysis plan (SAP) is meant to supplement the study protocol. Any deviations from this analysis plan will be described in the clinical study report.

1.1 Trial objectives

1.1.1 Primary Objective(s)

- To test for superiority of apalutamide monotherapy vs. LHRHa monotherapy in prostate cancer patients with BCR by comparing the mean change from baseline in quality of life (QOL) as measured by total FACT-P score over a period of 12 months of therapy.
- To test for non-inferiority of the combination apalutamide + LHRHa vs. LHRHa monotherapy in prostate cancer patients with BCR by comparing the mean change from baseline in QOL as measured by total FACT-P score over a period of 12 months of therapy.

1.1.2 Secondary Objectives

- To compare (a) apalutamide monotherapy vs. LHRHa monotherapy and (b) combination apalutamide + LHRHa vs. LHRHa monotherapy with regards to change over time in QOL as measured by EORTC QLQ-C30 and SHIM.
- To compare (a) apalutamide monotherapy vs. LHRHa monotherapy and (b) combination apalutamide + LHRHa vs. LHRHa monotherapy with regards to PSA modulation.
- To compare (a) APALUTAMIDE monotherapy vs. LHRHa monotherapy and (b) combination apalutamide + LHRHa vs. LHRHa monotherapy with regards to metabolic and hormonal effects.

1.1.3 Other Objectives

- To characterize the safety profile of apalutamide monotherapy and in combination with LHRHa.
- To conduct biomarker analyses from all 3 treatment groups.

1.2 Trial Design

This is a randomized, multicenter, open-label, 3-arm phase 2 clinical trial evaluating 12 months of treatment with luteinizing hormone releasing hormone agonist (LHRHa) monotherapy, apalutamide monotherapy, or the combination of apalutamide and LHRHa, in men with non-metastatic BCR prostate cancer with rapidly rising PSA levels after prior definitive therapy for localized prostate cancer. Enrollment of approximately 90 subjects (30 per arm) is planned for this study. Patients will be followed for safety and efficacy as per the schedule of assessments and will remain on study treatment until the time of PSA or radiographic progression or initiation of non-protocol therapy or subject/physician withdrawal from the study, whichever occurs first. Subjects will be stratified by PSADT (< 6 months vs. 6-12 months) and age (≤ 70 vs. > 70). There will be 2 periods of 12 months each in the 24-month-long treatment period: 1) an on-

therapy period lasting 12 months, during which time subjects receive randomly assigned protocol therapy, and 2) an off-therapy observation period also lasting 12 months. If there is no evidence of PSA or radiographic progression after 24 months from Day 1 of the on-treatment period, subjects will enter a follow-up period. Subjects will remain on study until the time of PSA or radiographic progression or initiation of non-protocol therapy or subject/physician withdrawal from the study, whichever occurs first. Patients who discontinue before completion of the on-therapy period in the absence of progressive disease will enter the off-therapy observation period of the study.

1.3 Statistical Hypotheses for Trial Objectives

1.3.1 Hypothesis 1

For men with non-metastatic, non-castrate prostate cancer who have rapidly rising PSA levels after definitive local therapy, treatment with 12 months of apalutamide monotherapy compared with 12 months of ADT in the form of LHRHa monotherapy will result in better preservation of QOL as measured by the FACT-P scale. Parallel and exploratory findings demonstrating comparable PSA suppression, and less negative impact on the metabolic profile (including measurements of fasting lipid profiles, insulin resistance, and bone mineral density) of subjects who receive apalutamide monotherapy as opposed to therapy with an LHRHa would form the preliminary basis for further definitive study of apalutamide monotherapy in biochemically relapsed prostate cancer.

1.3.2 Hypothesis 2

For men with non-metastatic, non-castrate prostate cancer who have rapidly rising PSA levels after definitive local therapy, treatment with 12 months of therapy with the combination of apalutamide + LHRHa, compared with 12 months of therapy with LHRHa alone, will not be associated with a clinically significant worsening of QOL as measured by the FACT-P scale. Parallel, exploratory findings suggesting more durable PSA suppression coupled with adequate serum testosterone recovery, favorable PSA modulation with respect to PSA nadir and time to PSA progression, along with acceptable safety data, would form the preliminary basis for larger clinical trials testing the combination of apalutamide plus LHRHa vs. LHRHa alone in the hormone sensitive prostate cancer disease setting.

1.4 Sample Size Justification

The expected mean decline in FACT-P score and within group standard deviation for the control arm treated with 12 months of LHRHa monotherapy are 4-8 and 8-12 points, respectively, based on prior studies of measuring QOL using FACT-P among men treated with ADT [1, 2, 3]. A change in total FACT-P score that is clinically meaningful and impacts treatment in prior studies ranges from 5-8 points depending on cancer subtype [4]. Approximately 30 subjects will be randomized to each of the 3 treatment arms for this comparison. Accounting for a dropout/questionnaire non-completion rate of 10%, this will allow for 27 evaluable subjects per study arm. For the comparison of the mean change in FACT-P score between apalutamide monotherapy and LHRHa monotherapy, this sample size has 80% power to detect an effect size of at least 0.86, corresponding to a difference of 7.5 points in mean 12 month change in FACT-P

score between treatment groups with a common standard deviation for the change in each arm of 8.7 which is similar to the reported standard deviation for LHRHa monotherapy. This is based upon a 2-group t test, using a bi-directional level of significance of 0.025 (adjusted for 2 comparisons). To test for non-inferiority in QOL with apalutamide + LHRHa compared with LHRHa monotherapy, inferior QOL is defined as a greater than 7-point difference in mean change in FACT-P score between the treatment groups and the common standard deviation is again assumed to be 8.7. This sample size has 82% power to reject the null hypothesis of a difference in mean score and accept the alternative hypothesis of non-inferiority with an effect size of at least 0.81, using a 2-group t-test with 2-sided α of 0.025.

1.5 Randomization and Blinding

1.5.1 Randomization

Upon verification of inclusion and exclusion criteria, eligible patients will be centrally randomized in a 1:1:1 ratio to apalutamide monotherapy, apalutamide + LHRHa, or LHRHa monotherapy. The randomization will be stratified as follows:

- PSADT (< 6 months vs. 6-12 months)
- Age at study entry (≤ 70 years vs. > 70 years)

Balance in treatment assignment will be achieved using a randomized block design. Randomization will be carried out via computer generated random assignment. All subjects must commence treatment within (5 calendar days) of randomization. Study sites will email the Eligibility Checklist to the sponsor to obtain the subject's treatment assignment. Once subject eligibility is confirmed by the sponsor, an email with the treatment assignment number will be provided to the study site.

1.5.2 Blinding

This is an open-label study.

2. GENERAL ANALYSIS DEFINITIONS

Study Day: For safety, study day will be calculated in reference to the date of first dose. Study Day 1 corresponds to the date the subject receives first dose of study drug. For efficacy analysis, Study Day will be calculated in reference to the date of randomization.

Cycle: For the purpose of the study, a treatment cycle is defined as 28 days. Subjects will begin taking study drug on Day 1 of Cycle 1. All subjects should be following a 28-day, 28-day, 35-day schedule for their monthly visit (i.e., the 1st post-Day 1 visit is scheduled for 28 days later, the 2nd post-Day 1 visit is scheduled for 28+28 days later, the 3rd post-Day 1 visit is scheduled for 28+28+35 days later, the 4th post-Day 1 visit is scheduled for 28+28+35+28 days later, etc).

Baseline Value: Unless otherwise specified, the baseline value will be defined as the closest measurement prior to or on the day of the first dose of study drug. Change from baseline will be defined as (post-baseline value – baseline value).

Treatment Duration: Treatment duration will be defined as the duration of time from the date of the first dose of study drug to the date of last dose of study drug.

Time to event: Time to event calculations will be defined as the time from randomization to the date of the event of interest. Time to event or duration of event endpoints will be based on the actual date of the event, not visit number or visit label.

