2.2.1 Day 1 of Study Treatment

Patients will return to study site for a history and physical exam including weight, measurement of serum PSA, and dispensing of study drug(s), including the first injection of LHRHa and 1-month supply of apalutamide for subjects randomized to those arms. Collection of optional samples (samples for banking, archival FFPE blocks or slides for transcriptome profiling (RNAseq), whole blood for RNA testing, and plasma for biomarker testing) should occur before pre-dose.

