2.2.2 LHRH Agonist

For subjects randomized to either the LHRHa monotherapy or the LHRHa + apalutamide combination treatment arms, the choice and schedule of LHRHa will be up to individual investigator's discretion and will be administered for a total of 12 months of therapy in the absence of disease progression or unacceptable toxicity. No change in dosing schedule of LHRHa will be permitted once the subject has commenced protocol therapy. For example, the use of every 3 month subcutaneously injected LHRHa would be administered on Day 1 and on Months 3, 6, and 9. The use of LHRH antagonists (ie, degarelix) will not be permitted. No dose reductions or interruptions of LHRHa will be permitted. If a subject does not receive a scheduled LHRHa injection within ± 7 days of the scheduled due date for injection, he will be removed from study. Subjects on the LHRHa monotherapy arm will not be allowed to crossover to receive apalutamide.

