4.3 Treatment Compliance and Extent of Exposure

The safety population will be used to summarize drug exposure, treatment compliance, and dose modifications by treatment group.

Treatment duration will be defined as the duration from the date of the first dose of study drug to the date of last dose of study drug. The number of tablets taken will be calculated based on the number of tablets dispensed at the study visits minus the number of returned tablets.

For apalutamide, the overall percent treatment compliance will be defined as the number of tablets taken during the study divided by the expected number of tablets, multiplied by 100. Each subject should be taking a maximum of 4 x 60-mg tablets of study drug per day while on the study. A subject's expected number of tablets will be calculated as the number of assigned tablets per day multiplied by treatment duration.

Choice of specific LHRHa to be used in this study will be per investigator discretion/site practice guidelines. Options include Eligard[®], Lupron Depot[®], Zoladex[®], or Trelstar[®]. Dosing schedule will be per individual investigator discretion. The use of LHRH antagonists (e.g. degarelix) will not be permitted. The LHRHa injections will be delivered either subcutaneously (Eligard[®], Zoladex[®]) or intramuscularly (Lupron Depot[®], Trelstar[®]) by a trained health care provider while on protocol therapy. Subjects with at least one dose modification and the reason for the dose modification will be summarized by treatment group.

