6. SAFETY

6.1 Adverse Events

The verbatim terms used in the electronic case report form (eCRF) by investigators to identify adverse events will be coded using the most current version of the Medical Dictionary for Regulatory Activities (MedDRA). Toxicities will be graded for severity according to NCI-CTCAE Version 4.03. All reported adverse events with onset during the On-therapy Period up to 30 days after the last dose of study medication will be included in the analysis.

Specifically, the following adverse events will be summarized:

- All adverse events
- Grade 3 or higher adverse events
- Serious adverse events
- Adverse events leading to discontinuation of treatment
- Adverse events leading to death

Summaries, listings, or subject narratives may be provided, as appropriate, for those subjects who died, who discontinue treatment due to an adverse event, or who experience a \geq Grade 3 or higher or a serious adverse event.

In addition, abnormal findings in physical exams and laboratory tests will be summarized.

All AEs reported during the AE reporting period (inclusive of the 30-day post last dose of study drug period) will be considered as treatment-emergent adverse events and will be summarized by treatment group as treated using all subjects in the safety population.

For each treatment group, AE incidence rates will be summarized with frequency and percentage by SOC and preferred term, with all subjects treated in that treatment group as the denominator, unless otherwise specified. In addition, AE incidence rates will also be summarized by severity and relationship to study drug. Treatment-related AEs are those judged by the Investigator to be at least possibly related to the blinded study drug. Subjects with multiple occurrences of events will only be counted once at the maximum severity to study drug for each preferred term, SOC, and overall. Deaths that occur within 30 days after the last dose of study drug are defined as on-study deaths.

AE onset date will not be imputed if it's completely missing. Partial AE onset date will be imputed as follows:

- If the AE onset date is missing day only, it will be set to:
 - the first day of the month that the AE occurred, if the month/year of the onset of AE is different from the month/year of the study treatment start.

-

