- the day of the study treatment start, if the month/year of the onset of AE is the same as month/year of the study treatment start but different from the month/year of the AE resolution date.
 - the day of the study treatment start or the day of AE resolution date, whichever is earlier if the month/year of the onset of AE and month/year of the study treatment start and month/year of the AE resolution date are same.
 - If the AE onset date is missing both day and month, it will be set to the earliest of:
 - January 1 of the year of onset, as long as this date is after the study treatment start
 - the day and month of the study treatment start, if this date is the same year as that the AE occurred.
 - the AE resolution date.

Summary tables of the following AEs will be provided:

- Overall summary of AEs: the number and percentage of subjects who experienced any AE, any serious adverse event (SAE), any treatment-related AE, any treatment-related SAE, any discontinuations due to an AE, and any deaths
- All AEs by SOC and preferred term All AEs by SOC, preferred term, and toxicity grade
- Grades 3 or 4 AEs by SOC and preferred term
- Treatment-related AEs by SOC and preferred term
- Treatment-related AEs by SOC, preferred term, and toxicity grade
- Treatment-related Grades 3 or 4 AEs by SOC and preferred term
- AEs that led to study drug discontinuation by SOC and preferred term. Study drug discontinuation will be determined from the treatment disposition CRF (where reason for discontinuation is “Adverse Event”) and the specific AE will be determined from the AE CRF page (where action taken is “Drug withdrawn”)
- AEs that led to study drug discontinuation by SOC, preferred term, and toxicity grade
- AEs that led to dose modification by SOC, preferred term, and toxicity grade
- All SAEs by SOC and preferred term
- All SAEs by SOC, preferred term, and toxicity grade
- Deaths will be summarized by time period (on-study vs. during follow-up) and cause of death.

Subject listings of all AEs by toxicity grade, Grades 3 or 4 AEs, all SAEs, AEs that led to study drug discontinuation, dose modification, and all deaths will be provided as well.

Narratives will be written for the following subjects in the final clinical study report:

- Subjects who die ≤ 30 days after the last dose of study drug
- Subjects who discontinue study drug due to treatment-emergent AE

- Subjects who experience a treatment-emergent SAE
- Subjects who experience seizure,

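### SAP first-to-last-dose rule sets no end of exposure for depot LHRHa: on the plan's 3-monthly example a completer counts as 273 of 364 days, and deaths on days 304–364 are labelled follow-up (minor)

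*SAP*

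**What the plan says.** SAP section 2 defines treatment duration as the "duration of time from the date of the first dose of study drug to the date of last dose of study drug". SAP section 4.3 repeats it for the exposure summary ("the duration from the date of the first dose of study drug to the date of last dose of study drug") and presents exposure by treatment group in the safety population.

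SAP section 6.1 uses the same last-dose date for deaths: "Deaths that occur within 30 days after the last dose of study drug are defined as on-study deaths". The table split follows from it: "Deaths will be summarized by time period (on-study vs. during follow-up) and cause of death". One of the narrative criteria is "Subjects who die ≤ 30 days after the last dose of study drug".

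LHRHa falls under these rules. The Protocol abstract lists it among the study drugs, and SAP section 2.2.1 describes Day 1 as including "dispensing of study drug(s), including the first injection of LHRHa and 1-month supply of apalutamide". The safety population requires at least one dose of study drug, so the LHRHa monotherapy arm can enter it only on that reading.

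SAP section 2.2.2 gives LHRHa for 12 months in total, with the schedule left to the investigator. Its illustration is that "every 3 month subcutaneously injected LHRHa would be administered on Day 1 and on Months 3, 6, and 9". Neither document says how long an injection counts as exposure.

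**The concern.** For a tablet taken daily, the last dose date and the end of treatment nearly coincide. For a depot they do not: the last injection is given one dosing interval before treatment ends. Applied literally, the SAP leaves that last interval out of the control arm's exposure and starts its 30-day death clock from the injection. The on-study/follow-up split of deaths then uses different calendar cuts in different arms, in a trial that has characterising safety as an objective. A programmer who adds the interval departs from the written definition; one who does not produces a control-arm exposure table at odds with the plan's own 12 months of therapy.

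A second defect sits in the same section and has nothing to do with depots. One sentence of SAP section 6.1 restricts the adverse event analysis to onset in the On-therapy Period plus a 30-day tail. Another treats every event in the reporting period as treatment-emergent, and SAP section 2.2.4 starts collection at consent. Events before first dose are excluded by the first and admitted by the second, equally in all arms.

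**Working it through.** **Inputs.** Visit calendar of 28, 28 and 35 days (SAP section 2); injections on Day 1 and at Months 3, 6 and 9, with a ±7-day window (SAP 2.2.2); daily apalutamide (SAP 2.2.3); death cut at last dose + 30 days (SAP 6.1); 30 subjects per arm. Days are counted from first dose as day 0; numbering the first dose as Day 1 adds one throughout.

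**Reproducing the 12 months.** One quarter is 28 + 28 + 35 = 91 days; four quarters are 4 × 91 = 364 days.

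**Duration as written.** The 3-monthly injections fall on days 0, 91, 182 and 273. Duration = 273 − 0 = 273 days, and 273/364 = 75%. The uncounted part is 364 − 273 = 91 days. After one injection, first dose and last dose are the same date, so duration is 0 days, although the next injection is not due until day 91.

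**Death cut as written.** 273 + 30 = day 303. The On-therapy Period runs to day 364, so days 304–364 (364 − 303 = 61 days) are on therapy but labelled follow-up. For apalutamide taken to Month 12, the cut is 364 + 30 = day 394. The plan's own Follow-up Period begins only at Month 25 (SAP 2.4).

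**Dependence on the depot.** Only the 3-monthly row is the plan's example; the others are assumed.

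| Injection interval | Last injection (= duration) | Share of 364 | Death cut | On-therapy days after cut |
|---|---|---|---|---|
| Monthly (assumed) | 329 | 90% | 359 | 5 |
| 3-monthly (plan's example) | 273 | 75% | 303 | 61 |
| 4-monthly (assumed) | 238 | 65% | 268 | 96 |
| 6-monthly (assumed) | 182 | 50% | 212 | 152 |

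The ±7-day window moves the 3-monthly figures to 266–280 days and a cut of 296–310.

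**Deaths relabelled.** If all 30 controls use a 3-monthly depot and are still followed at day 303, the time at risk is 30 × 61/365.25 = 5.0 person-years. At an assumed annual mortality of 1–5% (entry requires an estimated life expectancy above 5 years), this is 5.0 × 0.01 to 5.0 × 0.05 = 0.05–0.25 deaths.

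**Pre-dose adverse events.** Screening assessments fall within 14 days before randomization, and Day 1 within 5 days after it (Protocol 7.1, footnote 1). If consent is signed at the start of that window, 14 + 5 = 19 pre-dose days count as treatment-emergent under one section 6.1 sentence and none under the other.

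**The case against.** The strongest reply is that little depends on this. Treatment duration is descriptive. It enters a calculation only for apalutamide tablets, where the "expected number of tablets will be calculated as the number of assigned tablets per day multiplied by treatment duration", and there first-to-last-dose works. Completion and discontinuation of study treatment are reported separately (SAP 4.2), so a completer shown at 273 days would not be taken for an early stopper. The 3-monthly schedule is only an example, and a monthly depot leaves 5 days. All of this stands and keeps the point minor. It does not make the definition right: a stated rule gives a wrong control-arm figure on the plan's own example.

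Several stronger readings are tempting but not supported.

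- A reader might infer that adverse events in Months 10–12 are lost for LHRHa, making the arms' rates incomparable. The section 6.1 sentence on inclusion covers onset throughout the On-therapy Period, so on its natural reading those months are counted. What may differ is the tail (day 364 against day 394), which would add events to apalutamide, not hide them.
- A reader might infer that the combination arm is equally affected. Exposure is summarised by treatment group, and the last dose there is normally daily apalutamide near day 364. The arm is affected only if apalutamide stops early or exposure is tabulated by drug.
- A reader might infer that deaths disappear. They are relabelled. All are listed, and most would still get a narrative through the criterion for treatment-emergent serious events.
- A reader might stretch the pre-dose period to the 6- and 12-week scan windows. Protocol 7.3.3 places scan collection after consent and after eligibility on the laboratory and clinical parameters, which are themselves assessed within 14 days of randomization. The longer windows fit scans already in hand.

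One objection to the remedy also stands in part. A subject who stops LHRHa early without progression enters the Off-therapy Observation Period, and adding the interval counts him as exposed for part of it. That overlap must be stated.

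**Conclusion.** The point holds as a minor error in the SAP as written. For LHRHa monotherapy on the plan's 3-monthly example, 12 months of therapy is tabulated as 273 of 364 days and a single injection as 0 days. The on-study death cut falls 61 days before the On-therapy Period ends, against about day 394 for apalutamide. The size depends on the depots actually chosen, which the plan leaves open. The 0.05–0.25 relabelled deaths rest on all 30 controls using a 3-monthly depot and on an assumed mortality of 1–5% a year; longer intervals would widen the gap. No efficacy result changes, and nothing here shows that apalutamide would appear falsely safe. The conflict between the two treatment-emergent sentences is separate, affects all arms alike, and should be settled in the same edit.

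**What to change.** The change is for analysis only and leaves dosing untouched. For treatment duration, the on-study/follow-up death split and the death-narrative criterion, define end of treatment as follows.

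- **LHRHa monotherapy:** the earliest of last injection date plus that subject's dosing interval, Month 12, and start of non-protocol therapy or removal from study.
- **Apalutamide monotherapy:** the last apalutamide dose.
- **Combination:** the later of the two dates, also ended at the start of non-protocol therapy or removal from study.

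On the 3-monthly example this gives 273 + 91 = 364 days and a cut at day 394, matching apalutamide.

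Keep tablet compliance on apalutamide dose dates. A combination subject who takes every tablet, stops apalutamide at day 182 and continues LHRHa to day 364 has 4 × 182 = 728 expected tablets and 100% compliance; on the combined date it would be 4 × 364 = 1456 and 50%.

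Replace the two section 6.1 sentences with one: treatment-emergent means onset or worsening on or after first dose, through end of treatment + 30 days.

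The cost is SAP wording and one derived date per subject. There are three drawbacks. The dosing interval must be available for each subject, which neither document shows. Early LHRHa stoppers may be counted as exposed during the Off-therapy Observation Period. For those who do not enter that period, Protocol 7.1 footnote 7 requires recording only to 30 days after the last dose. With a 91-day interval the new window can close at last dose + 91 + 30 = 121 days, so required recording may end up to 121 − 30 = 91 days too soon. Flag their adverse event data as possibly truncated.
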